review the participant’s medical information and provide an influenza diagnosis based on clinical judgement. If probable influenza is diagnosed, the 98point6 provider will confirm that antiviral treatment is appropriate. If appropriate, drug eligible study participant will subsequently receive a single dose of BXM delivered to their household via rapid delivery service for therapy initiation within 48 hours of symptom onset. Concurrently, the ill individual will collect a Study Day 0 nasal swab sample that will be mailed back to the laboratory for further testing. Additional nasal swabs will be collected at Study Day 2-3 and Study Day 5-7. If influenza is not diagnosed, the ill individual will provide one self-collected or parent/permanent legal guardian-collected nasal swab specimen that will be mailed back to the laboratory for further testing, and the household will remain enrolled and all study participants in the household will continue to self-monitor for presence of symptoms. Once an eligible study participant receives BXM, no additional household members will be eligible to receive BXM; the household will be able to continue monitoring for onset of symptoms, as well as self-testing and swabbing when symptoms develops, but the household will no longer be able to receive BXM delivery.

Figure 1. Study schema

Symptom Table

Feeling Feverish	Muscle or Body Aches
Headache	Rash
Sore Throat or Itchy/Scratchy Nose	Runny/stuffy nose
Feeling More Tired Than Usual	Muscle or body aches
Nausea or Vomiting	Increased trouble with breathing
Ear Pain or Ear Discharge	Diarrhea

The study is being conducted in the Seattle, WA area over one influenza season. The goal is to have 250 households comply with full study procedures. Of these, 25% are estimated to have an individual in the household diagnosed with influenza based on estimates from previous household studies.^{23, 28-29}

A table for influenza attack rates by household size is provided below.

Household attack rate	Total households enrolled	Primary cases	Secondary cases (mean household size 5)	Secondary cases (mean household size 4)	Secondary cases (mean household size 3)
25%	250	63	45-96	34-72	23-48
20%	250	50	36-76	27-57	18-38
10%	250	25	18-38	14-29	9-19
Mean household size includes case.					
Secondary attack rate 18-38%, secondary cases presented as a range based on these high and low bounds. ³⁰⁻³²					

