A list of serious adverse events will be presented by shelter and by treatment v. intervention period. As defined in the study protocol, serious adverse events include death, a life-threatening reaction to the study drug (or placebo) or other study procedure, hospitalization, or significant or persistent disability or impairment. The incidence of SAE's (events/person-days of follow-up) will be presented both (1) overall and (2) by case v. non-cases. We will test for a difference in SAE rate between the two study periods (intervention v. control) using an exact Poisson test in R.

Baloxavir-resistant influenza transmission

Evidence of a strong intervention effect causing incidence of baloxavir-resistant influenza strains will be evaluated using linear mixed effects logistic regression. The unit of analysis will be influenza-positive tests, and the outcome will be binary: baloxavir-resistant or not baloxavir-resistant.

B5. Power sample size

Table 1. Sample size calculations: Number of clusters needed per arm for two-group cluster-randomized trial - Household intervention study

Effect size (% reduction in flu incidence)			
Power	0.30	0.40	0.50
0.80	57	84	129
0.90	76	112	172

All calculations above assume an ICC of 0.29, anticipated average (or actual) cluster size of 4, and a 15% transmission rate for flu.

Based on these calculations, an arm size of 250 households should be sufficient to detect a 30% reduction in flu incidence at 90% power.

B6. Endpoint Analyses

Primary Analysis

[figure not shown]
Question: Does this home-based self-test diagnostic tool and rapid treatment intervention lead to a large percentage of influenza-positive individuals initiating antiviral therapy within 48 hours of symptom onset?

Endpoint: Cumulative incidence of influenza virus infection

Measure of Association:
Cumulative Incidence (Attack Rate, Incidence Proportion)

$$\text{Cumulative Incidence} = \frac{\text{Number of participants that successfully initiate antiviral therapy within 48 hours of symptom onset (among participants who have a cough and self-test positive for influenza) during the October 2019-May 2020 influenza season}}{\text{Number of influenza-free participants at risk at } t_0 \text{ (baseline)}}$$

Relevant DAG

Exposure:

Exposed (Treatment) = Participants who develop cough and self-test positive
Unexposed (No treatment) = Participants who develop cough but self-test negative

Outcome:

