Success = Participant initiated on antiviral therapy within 48 hours of symptom onset
Failure = Participant is not initiated on antiviral therapy (**more than 48 hours** after symptom onset *or* participant **never** initiates antiviral therapy)

Table 1. Estimated secondary attack rates for planned 2019-2020 study aim on household transmission dynamics.

The study is being conducted in the Seattle, WA area over one influenza season. The goal is to enroll at least 250 (up to 1,000) households. Of these, 25% are estimated to have an individual in the household diagnosed with influenza based on estimates from previous household studies.^{23, 28-29}

A table for influenza attack rates by household size is provided below.

Household attack rate	Total households enrolled	Primary cases	Secondary cases (mean household size 5)	Secondary cases (mean household size 4)	Secondary cases (mean household size 3)
25%	250	63	45-96	34-72	23-48

20%	250	50	36-76	27-57	18-38
10%	250	25	18-38	14-29	9-19
Mean household size includes case.					
Secondary attack rate 18-38%, secondary cases presented as a range based on these high and low bounds.³⁰⁻³²					

Incidence Density

Using time-specific variables such as date of enrollment, weekly symptom diaries and questionnaires, Incidence Density (ID) will be calculated, defined with the following formula:

Incidence Density =

Number of participants that successfully initiate antiviral therapy within 48 hours of symptom onset (among participants who have a cough and self-test positive for influenza)

Total person-days

Model

The proportion of individuals that 1) test positive and 2) receive and initiate treatment within 48 hours of symptom onset using home-based self-test and delivery methods will be analyzed with a binomial regression GLMM with a log link. The outcome follows a binomial distribution, with the number of successes in a series of n independent Bernoulli trials, where each trial has probability of success p . Successes here are defined as an individual successfully initiated on antiviral therapy within 48 hours of symptom onset using home-based self-test to diagnose influenza and home delivery of antivirals. The model is defined below:

Incidence proportions of influenza will be presented in tables.

A formal statistical comparisons between study periods (control vs. intervention) will be performed using a Wald test of the hypothesis

$H_0: RR=1$

$H_a: RR \neq 1$

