The general form of the model (in matrix notation) is:

$$\mathbf{y} = \log\left(\frac{p}{1-p}\right) = \mathbf{X}\boldsymbol{\beta} + \mathbf{Z}\mathbf{u} + \boldsymbol{\epsilon}$$

Variable	Definition
\mathbf{y}	$N \times 1$ column vector, the outcome variable
\mathbf{X}	$N \times p$ matrix of the p predictor variables
$\boldsymbol{\beta}$	$p \times 1$ column vector of the fixed-effects regression coefficients (the β s)
\mathbf{Z}	$N \times q$ design matrix for the q random effects (the random complement to the fixed \mathbf{X})
\mathbf{u}	$q \times 1$ vector of the random effects (the random complement to the fixed $\boldsymbol{\beta}$)
$\boldsymbol{\epsilon}$	$N \times 1$ column vector of the residuals, that part of \mathbf{y} that is not explained by the model height

where each individual β value represents the change in log-odds of receiving and initiating treatment within 48 hours, that are associated with a particular demographic or clinical risk factor. A one-sided test with $\alpha = .05$ will be used. A table of the estimated Risk Ratios for a one unit increase in each covariate, given the other covariate values will be presented, along with the corresponding 95% confidence intervals, and p-values.

Data cleaning and analysis

All analyses will be performed in R version 3.6.1 using the package 'lme4.'

Secondary Analyses:

Question: How well does the self-test perform in comparison to the gold standard molecular test?

Sensitivity, specificity, PPV and NPV of the self-test will be calculated and compared to the gold standard molecular test. Table 2 (below) presents relevant formulas.

Table 2. Sensitivity, Specificity, PPV, and NPV of the Ellume Self-Test, SFS Household Intervention Study, 2019-2020 influenza season

Test Score	The Truth	
	Has Influenza	Does Not Have Influenza
Positive	True Positives (TP) a	False Positives (FP) b
Negative	False Negatives (FN) c	True Negatives (TN) d

$$\text{Sensitivity} = \frac{TP}{TP+FN} = \frac{a}{a+c} \quad \text{Specificity} = \frac{TN}{TN+FP} = \frac{d}{d+b}$$

$$\text{PPV} = \frac{TP}{TP+FP} = \frac{a}{a+b} \quad \text{NPV} = \frac{TN}{TN+FN} = \frac{d}{d+c}$$

Question: What is the association between influenza infection and: (1) influenza strain (by genetic sequencing) and (2) viral kinetics (maximum titer, duration viral RNA detection)?

Sensitivity analysis

Sensitivity analyses will be performed to explore the uniformity of any treatment effects found in the overall analysis.

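### SAP B6 labels self-test positives as treated and negatives as untreated; these labels do not follow who receives BXM, and a risk ratio built on them would not answer the primary question

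*SAP*

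**What the plan says.** SAP B6, Primary Analysis, sets up two groups: "Exposed (Treatment) = Participants who develop cough and self-test positive" and "Unexposed (No treatment) = Participants who develop cough but self-test negative". The outcome is "Success = Participant initiated on antiviral therapy within 48 hours of symptom onset". Failure covers both late initiation and never starting.

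The same section names its endpoint as the cumulative incidence of influenza infection. Its formula, however, counts on-time initiators, "among participants who have a cough and self-test positive for influenza", over everyone uninfected at baseline. The model paragraph repeats the restriction: "Successes here are defined as an individual successfully initiated on antiviral therapy within 48 hours of symptom onset using home-based self-test to diagnose influenza".

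Risk ratios appear in two places in B6, and neither refers to the two groups above. One is a hypothesis test: "A formal statistical comparisons between study periods (control vs. intervention) will be performed using a Wald test of the hypothesis", with RR = 1 as the null. The other is a table of risk ratios per unit of each demographic or clinical covariate.

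In the protocol (II. Study design), the tele-health provider is to "provide an influenza diagnosis based on clinical judgement". Section V (Onset of Symptoms) makes qualification for study drug depend on that consultation, and section X defines the drug-eligible, influenza-infected participant by it. Section III (Primary Outcome Measures) defines the primary outcome as one proportion. Its denominator is drug-eligible people positive on both the self-test and the laboratory test. Section XI gives the precision of a proportion and no comparator.

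**The concern.** A diagnostic result is given the name of a treatment, and receipt of treatment is then the outcome. A self-test negative whom the provider diagnoses and treats is filed under no treatment. A self-test positive who receives no drug is filed under treatment. That can happen because the provider does not consider treatment appropriate, because the person is drug ineligible, or because the household has already had a BXM recipient.

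The failure category adds to the difficulty. A self-test negative without influenza who is never prescribed BXM is scored as a failure of the strategy.

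The primary question asks what share of infected, eligible people start drug in time. If the exposure block were used to supply the contrast for the RR = 1 test, the headline result would be a comparison that the question does not ask for. Its value would depend on something unrelated to speed of delivery.

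**Working it through.** **The plan's own figure.** Protocol XI: 250 × 0.25 = 62.5, taken as 63 cases. Worst-case half-width = 1.96 × 0.5/√63 = 0.1235, which agrees with the stated ±0.12. This is the only precision figure for the primary proportion, and it belongs to a single group. Neither document gives a figure for a positive-versus-negative risk ratio.

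**Is there another contrast for the RR = 1 test?** The test names control and intervention periods. The protocol describes one cohort followed for one season under one strategy, with no control period. Within B6 the exposure block is the only definition of two groups. Using it for the test is therefore an inference, though an easy one to make.

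**Reading 1: the SAP's success definition.** Success requires a positive self-test, so P(success | negative) = 0 and RR = p/0, which is undefined for any p above 0. To see what a test would do, add 0.5 to each success count and to each failure count beyond it (so 63 becomes 63.5 with the success count raised by 0.5). Take 63 positives, 63 to 500 negatives (assumed) and p from 0.5 to 0.9 (assumed):

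- Lowest case, 32 of 63 positives and 0 of 63 negatives: RR = (32.5/63.5)/(0.5/63.5) = 65. SE = √(1/32.5 − 1/63.5 + 1/0.5 − 1/63.5) = 1.414. z = ln 65/1.414 = 2.95.
- Highest case, 57 of 63 positives and 0 of 500 negatives: RR = (57.5/63.5)/(0.5/500.5) = 906, z = 4.82.

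Every z exceeds 1.96. The null would be rejected by construction, even with only half of the positives treated in time.

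**Reading 2: treated negatives count as successes, as the protocol's prescribing route allows.** RR = p/q, where q is on-time initiation among self-test negatives. Neither document gives q. All inputs here are assumed, with p fixed at 0.80:

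| q | RR |
|---|---|
| 0.50 | 1.6 |
| 0.20 | 4 |
| 0.05 | 16 |
| 0.02 | 40 |

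The RR also moves with p: at q = 0.20, p = 0.5, 0.7 and 0.9 give 2.5, 3.5 and 4.5. The two influences cannot be separated. A programme with p = 0.9 and q = 0.50 has RR 1.8, while a worse one with p = 0.5 and q = 0.05 has RR 10.

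**The SAP denominator.** Suppose 63 cases and 250 households of 3 to 5 people, all uninfected at baseline (assumed), so 750 to 1,250 people. If every case were treated in time, the SAP fraction would be 63/750 = 8.4% down to 63/1,250 = 5.0%. The protocol proportion would be 100%. The SAP fraction mixes attack rate with timeliness.

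**The protocol's proportion.** With n = 63, 1.96 × √(p(1 − p)/63) gives 0.123, 0.113 and 0.074 at assumed p of 0.5, 0.7 and 0.9. The interval will be wider if some of the 63 are drug ineligible or self-test negative.

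**The case against.** The strongest reply is that the SAP specifies no risk ratio between self-test positives and negatives. The Wald test names periods, the model ratios are per covariate, and the quantity under the association heading is a single fraction. Control and intervention wording also appears in SAP B4 and C, so the test may be residual text rather than a plan to use the exposure block. The labels follow the mention of a causal diagram, and a figure in this section is not shown, so they may only annotate it. All of this stands. A reader might infer that the SAP's primary risk ratio is circular as written, but the documents do not support so firm a statement.

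Three further limits are fair:

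- Strict circularity (Reading 1) and the range 1.6 to 40 (Reading 2) rest on opposite premises and cannot both apply.
- It would be wrong to say that the RR has no bearing on timeliness, since it moves with p. Nor is an untreated positive miscounted for this outcome: the SAP scores never starting as failure, and the protocol keeps such people in the denominator if they are drug eligible and laboratory-confirmed.
- A reader might infer that safety tables would misassign BXM recipients. SAP B4 splits events by case status and by period and does not use these labels. The protocol's secondary comparisons already group BXM recipients by time of therapy.

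The SAP is dated 10/8/19 and protocol 3.1 January 14, 2020, which may explain the mismatch. It does not remove it, because an analyst would still find two different primary analyses.

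**Conclusion.** The point holds in a limited form. The group labels in B6 are wrong as descriptions of treatment, because under the protocol the provider's diagnosis leads to BXM. B6 then leaves a test of RR = 1 attached to periods that do not exist, with the exposure block as the only two-group definition available in that section.

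If that block is used, the contrast is uninformative for the primary question. The RR is undefined under the SAP's success definition. If treated negatives are counted, it depends jointly on the on-time proportion in positives and on an unknown rate in negatives (1.6 to 40 with the assumed inputs). That the block would be used is an inference, and the size is an illustration, not an estimate.

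The protocol's single proportion is well defined and its precision figure reproduces. The SAP should be brought into line with it before analysis.

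**What to change.** In SAP B6, Primary Analysis:

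- Delete the exposed/unexposed block, the *Measure of Association* heading and the control-versus-intervention Wald test of RR = 1.
- Replace the cumulative-incidence endpoint and its baseline-uninfected denominator with the proportion in protocol section III: on-time initiators among drug-eligible people positive on both self-test and laboratory test, with a 95% CI.
- Reconcile the success wording with the protocol's route to diagnosis and with that denominator.
- Keep the covariate risk ratios as an association analysis within that group.
- Define any treated/untreated grouping by recorded BXM ingestion. The protocol already collects it (section V, Onset of Symptoms, and Medication delivery and counseling).
- Report treated self-test negatives as a descriptive count.

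The cost is SAP wording only. No new data, visits or participants are needed.

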4. Additionally, one week later, the ill individual will complete day 7 of the illness questionnaire, which will ask information about respiratory and systemic symptoms, recent travel history, and absenteeism in 7 calendar days following the onset of a cough in the ill participant.

Immediately following the onset of an acute cough or 2 or more respiratory symptoms in a drug eligible participant, the following procedures will occur:

1. The person will self-test for influenza using the prepositioned home-testing kit as long as the following criteria are met:
 - Symptom duration <48 hours
 - Cough present or 2 or more respiratory symptoms present
 - i. Qualification for receipt of study drug will be determined based on a review of medical information with the tele-health provider. If the individual meets the required criteria (symptom duration <48 hours) and is diagnosed with probable influenza by a healthcare provider, this will trigger subsequent delivery of the intervention, if deemed appropriate.
2. Next, the ill individual will collect a nasal swab sample via self-swab or parent/legal guardian-swab as soon as possible. These specimens will then be packaged and shipping back to the laboratory via a delivery service for testing and further characterization. Additionally, the ill individual will complete day 0 of illness questionnaire in REDCap, which will ask information about respiratory and systemic symptoms, recent travel history, and absenteeism.
3. Concurrently, the participant will connect with a provider via the tele-health app previously downloaded on their smartphone. The provider will review the participant's symptoms and determine whether influenza infection is likely to be the underlying cause of the symptoms. If probable influenza is diagnosed, the tele-health provider will prescribe a weight-based dose of BXM. If antiviral treatment is not deemed appropriate by the tele-health provider, this information will be documented in the post-visit Care Plan for the study participant and subsequently shared with the study team.
4. Next, the study pharmacy will be notified that the participant is being prescribed BXM.

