Secondary aim: Determine the social and technical infrastructure that would be required to rapidly detect and interrupt influenza transmission at the household level and to determine whether a home-based self-test and antiviral delivery strategy would be feasible in the context of a pandemic.

Primary Objectives:

P1) To measure the proportion of individuals who are initiated on antiviral therapy within 48 hours of symptom onset using home-based self-test to diagnose influenza and home delivery of antivirals.

Secondary Objectives:

S1) Proportion of individuals who test positive for influenza using the home-based test within 48 hours of symptom onset

S2) Proportion of individuals who are delivered antivirals within 48 hours of symptom onset

S3) Symptom duration and severity among cases and household contacts

S4) Viral titer and duration of viral RNA detection among influenza-positive cases

S5) Cost effectiveness, assessed using health resource utilization and school and work absenteeism

S6) Emergence of antiviral resistance, assessed by genetic sequencing of influenza strains

B. Final Analysis Plan

This section describes the main statistical analyses that will be conducted on enrolled households at DSMB meetings and at the end of the study.

B1. Analysis Datasets

The Primary Dataset will consist of all individuals from enrolled households who enroll in the study, comprised of symptomatic (drug-eligible) individuals.

All eligible and enrolled households will be included in the study unless they meet one or more of the following exclusion criteria:

1. Previous documentation of an influenza infection prior to or during the annual influenza season in any household member prior to enrollment

At the participant level, enrolled individuals meeting any of the following criteria will be excluded from analysis (note: their household may still be eligible, as another eligible member of their household may still enroll):

1. The individual's informed consent is determined to be not valid
2. The individual has been double enrolled in the study. In this case, the individual's data will be used once.
3. No symptom questionnaire is collected.

B2. Variable definitions

[See Tables 1a-c for details]

B3. Baseline Tables and Study Conduct

Description of the main tables and statistical analyses

This section describes the main tables and statistical analyses. Metrics will be updated monthly and presented to the DSMB at each meeting.

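### SAP B6 sets self-test positives against self-test negatives on starting antivirals, a contrast that cannot answer the one-group primary question and scores untreated negatives as failures

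*SAP*

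**What the plan says.** **SAP B6, Primary Analysis.** The question is whether the strategy gets a large percentage of influenza-positive people onto antivirals within 48 hours of symptom onset. The section then defines two groups by self-test result: "Exposed (Treatment) = Participants who develop cough and self-test positive" and "Unexposed (No treatment) = Participants who develop cough but self-test negative".

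The outcome follows: "Success = Participant initiated on antiviral therapy within 48 hours of symptom onset" and "Failure = Participant is not initiated on antiviral therapy". The failure definition covers both a start after 48 hours and no start at all. It is not limited to self-test positives.

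**SAP B1.** The Primary Dataset is "comprised of symptomatic (drug-eligible) individuals", which is also not limited to self-test positives.

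**SAP B6, Model.** The RR=1 test is introduced as follows: "A formal statistical comparisons between study periods (control vs. intervention) will be performed using a Wald test of the hypothesis".

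**Protocol III, Primary Outcome Measures.** The primary outcome is a proportion. Its denominator is drug-eligible people who are both self-test positive and laboratory-confirmed. Protocol XI sizes the study by the width of a 95% CI for that kind of proportion. Neither section has a self-test-negative comparator.

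**Protocol V, Onset of Symptoms.** Receipt of study drug depends on the telehealth provider's diagnosis: "The provider will review the participant's symptoms and determine whether influenza infection is likely to be the underlying cause of the symptoms".

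**The concern.** A question about how large a percentage is needs an estimate in the people it concerns. Comparing self-test positives with self-test negatives asks something else: whether starting antivirals is associated with the self-test result. The two answers can diverge. A strategy that treats few positives on time can show a large ratio, because even fewer negatives are treated. A strategy in which providers treat most clinical influenza promptly, whatever the self-test shows, can give a ratio near 1.

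The failure rule adds a second problem. A self-test-negative participant to whom the provider prescribes nothing falls under failure as written, although that person is outside the group the question is about.

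The 'No treatment' label does not fit the protocol either. Because the provider's diagnosis governs prescribing, a self-test-negative participant could receive the drug.

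At stake is whether the SAP's primary result says anything about feasibility, and whether two analysts following the SAP and the protocol would report the same quantity.

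**Working it through.** **1. The plan's own figure.** Protocol XI: 250 × 0.25 = 62.5, rounded to 63 people with influenza. The half-width bound is 1.96 × 0.5/√63 = 0.123, which agrees with the stated ±0.12. This is a one-sample calculation and uses no comparator.

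**2. What the SAP text implies for successes in negatives.** There are two readings.

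- *Reading A.* Both numerators in B6 (cumulative incidence and incidence density) count starts only among participants who self-test positive. Self-test negatives then have zero successes by construction.
- *Reading B.* The Success definition carries no such limit, so a self-test negative who is prescribed the drug and takes it within 48 hours is a success.

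**3. Reading A: no successes in negatives.** The standard error of log RR for x/n₁ v y/n₀ is √(1/x − 1/n₁ + 1/y − 1/n₀). At y = 0 the term 1/y is infinite, so the Wald test is undefined. A log-link binomial fit to 50/63 v 0/190 returned a standard error of about 15,600 and p = 0.999, although 79% of positives were treated on time. Fisher's exact test, which the SAP does not specify, goes the other way. For 3/63 v 0/190, p = (63 × 62 × 61)/(253 × 252 × 251) = 0.015, so it rejects with 4.8% of positives treated.

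**4. Reading B: some negatives treated.** Inputs are n₁ = 63 (Protocol XI) and n₀ = 190. The value of n₀ and all uptake rates are assumptions, because the documents give none. Rejection probability is the sum over all (x, y) of Bin(x; 63, p₁) × Bin(y; n₀, p₀), taken where |log RR|/SE > 1.96. Tables with a zero count are scored as not rejecting.

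| Positives v negatives started within 48 h | n₀ = 63 | n₀ = 190 | n₀ = 400 |
|---|---|---|---|
| 20% v 2% | 0.64 | 0.97 | 1.00 |
| 20% v 10% | 0.31 | 0.54 | 0.62 |
| 30% v 20% | 0.23 | 0.40 | 0.46 |
| 10% v 5% | 0.09 | 0.29 | 0.36 |
| 80% v 80% | 0.05 | 0.05 | 0.06 |

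The 0.64 in the first row partly reflects empty comparators: the chance of no successes in 63 negatives at 2% is 0.98⁶³ = 0.28.

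The SAP writes a two-sided alternative but also says "A one-sided test with $\alpha = .05$ will be used". One-sided, the n₀ = 190 values for 20% v 2%, 20% v 10% and 80% v 80% are 0.98, 0.65 and 0.07.

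The first two rows have the same 20% uptake in positives, yet rejection moves from 0.97 to 0.54 at n₀ = 190. The last row has four times that uptake and almost never rejects.

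**5. The one-group alternative at n = 63.** The normal-approximation half-width 1.96 × √(p(1−p)/63) is 0.123 at p = 0.5, 0.099 at 0.8 and 0.074 at 0.9. The widest Wilson half-width, at p = 0.5, is 1.96 × 0.5/√(63 + 1.96²) = 0.120. The exact (Clopper-Pearson) interval is slightly wider, about 0.129 at 32/63.

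**The case against.** **No sentence in the SAP tests exposed against unexposed.** The RR=1 test is worded for control and intervention periods, and the other ratios and p-values attach to demographic or clinical factors. Protocol XI lists those factors, and self-test result is not among them. This stands. Applying the test to the exposure contrast is an inference. It is drawn because the protocol describes no control period and these are the only participant groups B6 defines for this outcome.

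**A reader might infer that RR=1 would be rejected almost regardless of feasibility.** The documents do not support that. With no successes in negatives, the specified test breaks down instead of rejecting. With moderate uptake in negatives, rejection is far from automatic (0.54, 0.40 and 0.29 in the middle rows at n₀ = 190). Provider-based prescribing makes such uptake possible.

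**A reader might also infer a quantified dilution of the success rate.** For example, 80% of 63 positives with 190 untreated negatives gives 0.8 × 63/(63 + 190) = 20%. No denominator in the SAP is positives plus negatives. The stated ones are participants at risk at baseline and person-days. The failure rule is wrong in scope, but this figure is not a forecast of what would be reported.

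**The block may be labels for a missing diagram.** It follows a DAG heading, and a figure is absent from the text available here. That is possible. The definitions are still printed as the exposure and outcome of the primary analysis.

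**The protocol is later** (January 2020, against October 2019 for the SAP) and already defines the one-group proportion. That supplies the repair. But neither document says the protocol supersedes the SAP here, and the SAP holds the detailed model.

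**Conclusion.** The point holds in a limited form. The exposure definitions in SAP B6 do not fit the primary question, the failure rule reaches people outside it, and both conflict with Protocol III, V and XI. This follows from the text alone and does not depend on any simulated rate.

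The consequence for a p-value is conditional. If the RR=1 test were applied to this contrast, its result would be governed largely by uptake in self-test negatives, which the documents do not give. With 63 positives and an assumed 190 negatives, it ranges from undefined, through 0.97 and 0.54 at the same 20% uptake in positives, to 0.05 when 80% of both groups start on time. The supportable conclusion is that the p-value would not track feasibility. The documents do not support saying that it would nearly always reject.

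The defect is separate from the reference to study periods and from the baseline-at-risk denominator: correcting those two would leave the exposure block and the unrestricted failure rule in place.

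**What to change.** In SAP B6:

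- Delete the Exposed and Unexposed definitions, and state that no ratio or test compares self-test positives with self-test negatives.
- Apply Success and Failure only to members of the denominator in Protocol III: drug-eligible, self-test positive and laboratory-confirmed.
- State the primary analysis as a one-sample proportion with a Wilson or exact 95% CI. If n = 63, the widest half-width is 0.120 (Wilson) or about 0.129 (exact), in line with Protocol XI.
- Report antiviral starts among self-test negatives descriptively, to show how providers acted relative to the test.

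Fixing in advance a percentage that counts as 'large', to set against the lower confidence limit, is optional. Protocol XI frames the objective as precise estimation, which does not require a threshold.

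The cost is SAP wording: no new data and no added participants. What is lost is a comparison that does not bear on the primary question.
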